**NCT05479123**

**Version Date: 06/02/2022**

**Protocol Title:** Assessing the Impact of Dosage Frequency of Propranolol on Sleep Patterns in Patients with Infantile Hemangiomas.

**Principal Investigator:** [name]

**Co-Investigators:** [name], [name], [name], [name], [name], [name]

**Sample Size:** 174

**Number of Sites:** Two study sites – Pediatric Plastic Surgery Clinic at the University of Texas Health Sciences Center at Houston and Dermatology Clinic at the University of Texas Health Sciences Center at Houston

**Study Duration:** Three years

**Subject Duration:** Up to age 18 months

**Version:** 1.4

**Most Recent Revision** 2/7/2022

---

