Overall, oral beta blockers have been the mainstay treatment for hemangiomas, but their association with sleep disturbances has continued to frustrate parents. Propranolol exhibits strong penetration into the blood brain barrier due to its lipophilicity. This penetration is likely exaggerated by the increased permeability of the blood brain barrier in infants (Vivas-Colmenares et al., 2015). Pediatric patients are thus at even higher risk of CNS side effects such as sleep disturbance and agitation. Parent reports of sleep impairments includes nightmares, insomnia, restlessness, increased waking, and overall sleep disturbance (Xerfan et al., 2020). While these sleep disturbances may be considered a minor side effect, the issue is cited as the most common reason for early discontinuation of propranolol (Ji et al., 2018).

The standard dosing regimen for oral propranolol for the treatment of infantile hemangiomas is twice a day (BID) dosage. In our multidisciplinary vascular anomalies clinic, parents of infants on propranolol for hemangiomas are queried at each visit regarding side effects. If a parent discusses concerns regarding sleep patterns, our standard protocol is to alter the regimen to three times a day (TID) dosage. While this seems to improve the sleep symptoms, there is no evidence to support this dosing schedule. The purpose of this study is therefore two-fold:

1. Assess the baseline sleep pattern disruption for patients starting oral propranolol at the standard BID dosing regimen compared to the control (timolol) group.
2. Determine if there is a significant improvement in the sleep patterns in infants taking oral propranolol on the TID dosing regimen versus the control (timolol) group.

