**Sample Size:**

A sample size calculation was performed using best estimates in the literature provided by Theiler et al. (Theiler et al., 2021). Primary outcome was defined as number of awakenings per

night of sleep at 6 months of time on propranolol. In the Theiler et al study, patients on propranolol had 0.26 +/- 0.09 vs control patients of 0.21 +/- 0.1 awakenings per night. Utilizing a two-tailed analysis, we anticipate enrollment of 58 patients per treatment arm, giving our study 80% power with alpha 0.05. Given our number of annual patients (approximately 60 per year), we anticipate this study to be performed in 3 years. A concurrent Bayesian analysis will be performed.

We will analyze the data as two separate studies, each using the control (timolol) group as the reference. The BID propranolol group will be compared to the control group, as well as the TID group compared to control. This will allow us to see the effective change of sleep awakenings in each dosage group compared to control.

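### The 80% power is attached to 58 infants enrolled per arm, but 58 is the number that must be analysed at month 6, and nothing is allowed for missing surveys

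*Combined protocol and SAP*

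**What the plan says.** The Sample Size section takes its inputs from a published cohort: "patients on propranolol had 0.26 +/- 0.09 vs control patients of 0.21 +/- 0.1 awakenings per night". It continues, "Utilizing a two-tailed analysis", to the statement "we anticipate enrollment of 58 patients per treatment arm, giving our study 80% power with alpha 0.05". The title page gives "Sample Size: 174". The same section plans two comparisons, BID propranolol against timolol and TID propranolol against timolol, so each is 58 against 58. The Primary Outcome section fixes both at six months on therapy.

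Four other places bear on how many infants will have that value:

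- **Sleep Survey.** The questionnaire (BISQ) is given at visits every three months. Each visit is described as an occasion on which it can be given, and nothing is said about a missed one.
- **Background and Significance.** Of sleep disturbance it says "the issue is cited as the most common reason for early discontinuation of propranolol".
- **Study Population.** Entry is open to any infant under 18 months of age.
- **Follow up and Study Termination** (under Sleep Survey). Medication and study participation end at 18 months of age.

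No section gives an expected loss rate, an evaluable number, an inflation of the sample size or a way to handle a missing month-6 survey.

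**The concern.** Power depends on how many infants contribute a value to the comparison, whereas the plan attaches it to how many are enrolled. The two are equal only if every enrolled infant supplies a month-6 BISQ. If 58 already contained a margin, the wording would be harmless. If 58 is the bare minimum, the stated 80% describes a best case and is presented as the expected one.

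The figure matters because it is the only basis given for the size of the trial, and it will be used to interpret a non-significant result in either comparison.

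**Working it through.** **Inputs, all from the Sample Size section.** Difference 0.26 − 0.21 = 0.05 awakenings per night; spreads 0.09 and 0.10; two-tailed alpha 0.05; power 80%; 58 per arm. The section does not say what its ± means. I read it as a standard deviation, which is the reading that reproduces 58.

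**Step 1: reproduce the plan's figure.**

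Pooled SD = √[(0.09² + 0.10²)/2] = √[(0.0081 + 0.0100)/2] = √0.00905 = 0.0951.

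Normal approximation: n = 2 × [0.0951 × (1.960 + 0.842)/0.05]² = 56.8, so 57 per arm.

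Two-sample t test: power comes from the noncentral t distribution with 2n − 2 degrees of freedom and noncentrality 0.05/[0.0951 × √(2/n)]. At n = 58 the noncentrality is 2.83 and power is 80.1%. At n = 57 power is 79.4%. The smallest n reaching 80% is therefore 58, the plan's own number. A Welch test gives the same n.

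**Step 2: look for a margin.** 3 × 58 = 174, the total on the title page. The per-arm figure is the t-test minimum and the total is three times that minimum, so neither contains an allowance.

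**Step 3: sources of missing month-6 values that the documents themselves contain.**

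- The only data source is a questionnaire given at a three-monthly visit, so a missed visit or an uncompleted form leaves no value.
- Early stopping of propranolol is acknowledged. The outcome is defined at six months on therapy, and the plan does not say whether infants who stop are still surveyed.
- 18 − 6 = 12. An infant who starts after 12 months of age leaves treatment before six months on therapy. The entry criteria admit such infants, and the documents do not say how many are expected.

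**Step 4: power at smaller evaluable numbers.** The missing rates are assumptions, taken as equal in both arms, with 58 × (1 − rate) rounded down. The true difference stays at 0.05 and the pooled SD at 0.0951.

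| Assumed missing | Evaluable per arm | t-test power | Difference detectable with 80% power |
|---|---|---|---|
| 0% | 58 | 80.1% | 0.050 |
| 5% | 55 | 78.0% | 0.051 |
| 10% | 52 | 75.6% | 0.053 |
| 15% | 49 | 73.1% | 0.054 |
| 20% | 46 | 70.3% | 0.056 |
| 30% | 40 | 64.1% | 0.060 |

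The last column solves the Step 1 power expression for the difference, with power set to 80%.

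**The case against.** The strongest reply is that the calculation contains no error. The 58 reproduces, 3 × 58 agrees with 174, and the shortfall appears only once a loss rate is assumed that the documents do not supply. The clinic's own statements also point towards good retention: the Follow up text says all patients stay on medication until 18 months of age and are seen every three months, and Safety Measures reports no adverse effects in over 1000 patients. This stands in part. The fault is a missing allowance, not wrong arithmetic, and the size of the loss cannot be fixed from the documents. The retention statements do not show that every parent completes the month-6 survey, and they do nothing for an infant too old at entry to reach month 6.

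A reader might draw three stronger conclusions that the documents do not support.

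- *That 80% is lost as soon as one infant per arm is missing.* With the t test the drop is 80.1% to 79.4%, or 0.7 points, which is immaterial for a planning figure. The plan names no test, and the normal approximation still gives 80.1% at 57 per arm.
- *That loss will be heavier in the propranolol arms.* The Background text ranks reasons for stopping. It gives no rate of stopping and no comparison with timolol, and stopping a drug is not the same as missing a survey. It also says the clinic's usual response to sleep concerns is to change the regimen. The point here does not need unequal loss.
- *That accrual leaves only 6 infants (3 × 60 − 174, or 3.3%) for refusal, ineligibility and loss.* The plan says "Given our number of annual patients (approximately 60 per year), we anticipate this study to be performed in 3 years". It does not say whether 60 is before or after eligibility and consent, and an infant lost after enrolment is already among the 174. No margin can be derived from that figure.

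**Conclusion.** The point holds. The plan credits 80% power to 58 enrolled infants per arm when its own inputs require 58 analysed, and it makes no allowance for missing month-6 surveys although its own text makes some foreseeable. At assumed missing rates of 10%, 20% and 30%, power per comparison is about 76%, 70% and 64%.

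These figures rest on reading ± as a standard deviation, a two-sample t test at a two-sided 0.05 for each comparison, equal loss in the two arms, and loss unrelated to the outcome. The normal approximation gives values about one to two points higher at the same missing rates and does not change the conclusion. What remains unknown is the actual missing rate, which the sponsor can estimate and this review cannot. The design can stand; the unconditional 80% cannot.

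**What to change.** In the Sample Size section, separate enrolled from evaluable infants:

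1. Say that 58 per arm gives 80% power for each comparison only if all 58 supply a month-6 BISQ.
2. State the missing rate expected from the clinic's own follow-up records, counting infants who would be too old at entry to reach six months on therapy before 18 months of age.
3. Quote the power at the resulting evaluable number as the study's power, with the difference detectable at 80%. For example, with 10%, 20% or 30% missing, power is about 76%, 70% or 64%, and the detectable difference is about 0.053, 0.056 or 0.060.

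The cost is about two sentences and a less favourable stated power. No extra enrolment is required. If the sponsor prefers to keep 80%, the alternative is to enrol 58/(1 − rate) per arm: 58/0.90 gives 65 (195 in total) and 58/0.80 gives 73 (219 in total). At the stated 60 a year, those totals would take longer than three years.

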**Hypothesis:**

We anticipate that patients receiving the TID dosing regimen of oral propranolol will demonstrate fewer sleep awakenings compared to the control group than the BID dosing regimen compared to the control.

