**Primary Outcome:**

1. Using the BISQ, number of sleep awakenings per night between the control (timolol) group and the BID propranolol group at 6 months on therapy.
2. . Using the BISQ, number of sleep awakenings per night between the control (timolol)group and the TID propranolol group at 6 months on therapy.

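### One 80% power figure, based on a single 0.05 difference, covers both primary comparisons, although the hypothesis expects a smaller difference for timolol vs TID than for timolol vs BID

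*Combined protocol and SAP*

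**What the plan says.** All references are to the combined protocol and SAP.

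- **Sample Size** gives one set of planning values from a cited cohort: "patients on propranolol had 0.26 +/- 0.09 vs control patients of 0.21 +/- 0.1 awakenings per night". It names no regimen. From these, with a two-tailed test, it states "we anticipate enrollment of 58 patients per treatment arm, giving our study 80% power with alpha 0.05". It then sets out two control comparisons, BID against timolol and TID against timolol, and gives no separate effect size for TID.
- **Primary Outcome** lists both comparisons. The second is the "number of sleep awakenings per night between the control (timolol)group and the TID propranolol group at 6 months on therapy".
- **Hypothesis** expects that patients on TID "will demonstrate fewer sleep awakenings compared to the control group than the BID dosing regimen compared to the control".
- **Background and Significance** says: "The standard dosing regimen for oral propranolol for the treatment of infantile hemangiomas is twice a day (BID) dosage". It also reports the clinic's impression that switching to TID helps sleep, and says that this schedule lacks supporting evidence.
- **Prescription** treats topical timolol as raising no sleep concern.

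**The concern.** A single planning difference is used for two comparisons that the plan itself expects to differ in size. If the literature value of 0.05 describes propranolol as ordinarily given (BID), and TID is gentler on sleep, the expected timolol-vs-TID difference is below 0.05 and the power of that comparison is below 80%.

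This bears on how the trial will be read. Research Question and PICO ask about TID against BID, but every comparison specified under Primary Outcome and for the sleep measures under Secondary Outcomes is against timolol. The benefit of TID will therefore tend to be inferred from the pair of control comparisons. If BID differs significantly from timolol and TID does not, a reader who believes that both comparisons had 80% power may conclude that TID removes the sleep effect. With lower power, that pattern can easily arise while a real TID effect remains.

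**Working it through.** **Inputs.** From Sample Size: means 0.26 and 0.21, spreads 0.09 and 0.10, two-sided alpha 0.05, 58 per arm. The spreads are read as standard deviations; the text does not say so, but this reading reproduces the stated sample size.

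**Step 1: reproduce the plan's figure.**

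- Difference: 0.26 − 0.21 = 0.05.
- Pooled SD: √((0.09² + 0.10²)/2) = √0.00905 = 0.0951.
- Normal approximation: n = 2 × (1.960 + 0.842)² × 0.00905 / 0.05² ≈ 56.8, so 57 per arm.
- Two-sample t test (noncentral t): 58 per arm, with power 80.1%. This matches the plan.

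An SD of 0.10 in both arms would need 64 per arm by the t test, and a one-sided test 45 by the normal approximation. The two-sided, pooled-SD version is the one that fits.

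**Step 2: slack.** The standard error of a difference is 0.0951 × √(2/58) = 0.01767. Solving for the true difference that gives 80% power at 58 per arm yields 0.0495 (normal) or 0.0499 (t test). In practice, any true difference below 0.05 gives less than 80%.

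**Step 3: the ordering in the Hypothesis.** Write B for the BID excess over timolol and T for the TID excess. The Hypothesis says T < B and gives neither size. If B = 0.05 and TID lies between timolol and BID, then 0 ≤ T < 0.05.

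**Step 4: power for timolol vs TID over a range of T.** The documents give no value of T, so the values below are assumptions. The noncentrality is T / 0.01767, with 114 degrees of freedom.

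| Assumed T | Noncentrality | Power (t test) |
|---|---|---|
| 0.050 | 2.83 | 80.1% |
| 0.045 | 2.55 | 71.4% |
| 0.040 | 2.26 | 61.2% |
| 0.035 | 1.98 | 50.2% |
| 0.030 | 1.70 | 39.1% |
| 0.025 | 1.42 | 28.9% |

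**Step 5: what a null result would mean.** If TID halved a BID excess of 0.05 (T = 0.025), timolol vs TID would be non-significant in about 100 − 28.9 = 71% of trials although half the disturbance remained. The 95% confidence interval has a half-width of about 1.98 × 0.01767 = 0.035. An observed difference of 0.025 would give an interval from about −0.010 to 0.060, which includes both zero and the full planning difference of 0.05.

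**The case against.** The strongest reply is that the power statement is not false. Power is always stated at a chosen difference, and 58 per arm gives 80% at 0.05 for either comparison, TID included. Sample Size never says that 0.05 is the expected TID effect. This stands. A reader might infer that the 80% belongs to timolol vs BID alone, or that 58 was miscalculated; the documents support neither.

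Second, the link between 0.05 and BID is an inference. Sample Size says only propranolol, and the cited cohort's regimen is not given. A reader might infer that every TID effect compatible with the Hypothesis is below 0.05. That is too strong: the Hypothesis only orders the two effects, and a BID excess of 0.07 with a TID excess of 0.05 satisfies it and keeps 80% power. The BID reading is still the better supported one, since Background and Significance calls BID standard and Potential Benefits says that information on alternative dosing is not in the literature.

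Third, the Hypothesis is loosely worded, and the second purpose in Background and Significance speaks of improvement on TID relative to timolol. If TID were expected to beat timolol by 0.05 or more, a two-sided test would lose no power. This is possible on the words, but it fits poorly with timolol being treated as neutral for sleep; TID between timolol and BID is the natural reading.

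Fourth, a reader might take from the table that power is well under half. That needs a difference clearly below 0.035, and nothing in the plan points to such a value.

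Finally, the Hypothesis does not require a significant timolol-vs-TID difference, and a concurrent Bayesian analysis is mentioned. Both are true, but that analysis is not specified, so it does not yet guard against misreading a null result.

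**Conclusion.** The point holds conditionally. An unqualified 80% is stated for two primary comparisons that the plan expects to differ in size. Timolol vs TID falls short of 80% under the trial's own hypothesis on two assumptions: that 0.05 represents the BID regimen, and that TID lies between timolol and BID. Both are reasonable readings; neither is stated outright. The direction of the shortfall then follows, because the design has almost no slack at 0.05. Its size cannot be fixed from the documents: the illustrative range runs from 71% at 0.045 to 29% at 0.025.

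The sample size calculation itself is correct. The fault lies in what the 80% is allowed to imply for the second comparison, and the text should be changed because a null result there is open to misreading.

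**What to change.** In Sample Size, state that:

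1. 58 per arm gives 80% power for either primary comparison only at a true difference of about 0.05 awakenings per night (SD 0.095).
2. The Hypothesis expects a smaller difference for timolol vs TID, so lower power is expected there. Any figures should be labelled as illustrations under assumed differences: 71% at 0.045, 61% at 0.04, 39% at 0.03 and 29% at 0.025.
3. A non-significant timolol-vs-TID result will not be read as showing that TID removes the sleep effect, and that difference will be reported with its confidence interval.

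It would also help to say which regimen the cited 0.05 is taken to represent.

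Keep the sample size. The cost is a few sentences; outcomes, tests and treatment do not change. The downside is that the stated power for the second primary comparison becomes less favourable.

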**Research Question:**

In patients with infantile hemangioma, does three times a day (TID) dosing versus twice a day (BID) dosing of propranolol significantly improve subjective sleep scores?

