## PICO

P: In patients with infantile hemangiomas  
I: does TID dosing of oral propranolol versus  
C: standard BID dosing of oral propranolol  
O: result in a significant improvement in subjective sleep scores

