**Study Design:**

Prospective, single center, randomized controlled trial – parallel groups

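### TID versus BID is the stated question and the only randomised contrast, yet every planned sleep comparison and the stated 80% power concern propranolol versus non-randomised timolol

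*Combined protocol and SAP*

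**What the plan says.** The title is "Assessing the Impact of Dosage Frequency of Propranolol on Sleep Patterns in Patients with Infantile Hemangiomas". The Research Question asks: "does three times a day (TID) dosing versus twice a day (BID) dosing of propranolol significantly improve subjective sleep scores". The PICO names the comparator as "C: standard BID dosing of oral propranolol".

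The Hypothesis is framed through the control group: TID patients "will demonstrate fewer sleep awakenings compared to the control group than the BID dosing regimen compared to the control".

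The rest of the plan compares each regimen with timolol only. The second purpose in Background and Significance concerns "infants taking oral propranolol on the TID dosing regimen versus the control (timolol) group", and the first pairs BID with timolol. The second primary outcome is the "number of sleep awakenings per night between the control (timolol)group and the TID propranolol group at 6 months on therapy", and the first is its BID counterpart. Item 1 of the Secondary Outcomes uses the same two pairings. The analysis paragraph under Sample Size says "We will analyze the data as two separate studies, each using the control (timolol) group as the reference".

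Study Design calls the study a "Prospective, single center, randomized controlled trial". Under Prescription, only infants with larger or multiple lesions are randomised, to BID or TID. Infants with one lesion under 2 cm receive timolol and enter as controls without randomisation.

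**The concern.** The question and the analysis concern different contrasts. A team that followed the plan exactly would finish with two comparisons against timolol and no planned inference on TID versus BID.

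The omitted contrast is the only one that randomisation protects. Both primary contrasts compare groups that differ by design in lesion size and number. The protocol does not say how these relate to sleep, so the direction and size of any confounding are unknown.

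Readers will be tempted to set the two results side by side and treat a significant result in one arm but not the other as a dosing effect. That is not a test of TID versus BID. The study is also open label, so a TID versus BID analysis added once data have been seen would be post hoc.

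**Working it through.** **1. Which contrast each section addresses**

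| Section | Contrast |
|---|---|
| Research Question, PICO | TID vs BID |
| Hypothesis | (TID − control) vs (BID − control), which equals TID − BID because control cancels |
| Background purposes, Primary Outcome, Secondary Outcomes item 1, analysis paragraph | BID vs timolol; TID vs timolol |
| Power inputs (Sample Size) | propranolol vs control |
| Randomised (Prescription) | BID vs TID only |
| Bayesian sentence (Sample Size) | none named |

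No section gives a test, an interval or a commitment to report an estimate for TID versus BID on any specified sleep outcome.

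**2. Reproducing the plan's figure**

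Inputs from Sample Size: means 0.26 (SD 0.09) and 0.21 (SD 0.10), two-sided alpha 0.05, 58 per arm.
- Pooled SD = √((0.09² + 0.10²)/2) = √0.00905 = 0.0951.
- Two-sample t-test for 0.05: 57.8 per arm for 80% power, so 58; power at 58 per arm is 80.1%.
- 3 × 58 = 174, the stated total.

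The sample size is arithmetically right for propranolol versus control.

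**3. TID versus BID at 58 per arm**

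The protocol gives no TID–BID difference, so the differences below are assumptions: the whole 0.05 gap, or half of it. SE = SD × √(2/58); half-width = t(114) × SE, with t = 1.981.

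| SD | SE | 95% CI half-width | Power for 0.05 | Power for 0.025 | Detectable at 80% power |
|---|---|---|---|---|---|
| 0.09 | 0.0167 | 0.033 | 84% | 32% | 0.047 |
| 0.10 | 0.0186 | 0.037 | 76% | 27% | 0.052 |

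The detectable difference is about the entire gap assumed between propranolol and control.

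**4. If the SD is larger (assumptions)**

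- SD 0.15 or 0.20: power for 0.05 is 43% or 27%; half-width 0.055 or 0.074.
- If awakenings are recorded as whole numbers per infant (no response format is given), a mean m below 1 forces an SD of at least √(m(1 − m)): 0.41 at m = 0.21 and 0.44 at m = 0.26. Power for 0.05 is then about 10% to 9%, and the half-width about 0.15 to 0.16.

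**5. Why the two timolol comparisons cannot stand in**

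- *Comparing significance.* Simulation of 400,000 trials used normal arm means, a shared control, the protocol's SDs, 58 per arm and the same true effect (+0.05) in both regimens. One arm was significant and the other not in about 21% of trials. A direct TID versus BID test rejected in 5%, as it should.
- *Subtracting the two differences.* The point estimate is right, because control cancels. If the two results are treated as independent, the control variance is counted twice. The SE relative to the direct SE is √((0.10² + SD²)/SD²) = 1.49 at SD 0.09 and 1.41 at SD 0.10.

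**The case against.** The best defence is that the two purposes in Background and Significance are both control-referenced, and that the outcomes and analysis follow them consistently. The conflict could then be settled the other way, by narrowing the Research Question and PICO. That would be coherent on paper, but randomisation would then serve no planned comparison.

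A second defence is that the Hypothesis already implies TID versus BID, and that anyone with arm means, SDs and counts can compute the interval. This is true, and nothing suggests that arm-level results will be withheld. What is missing is prespecification: the two control-referenced results alone do not yield the interval, and the plan commits to nothing more. The plan does not propose subtracting them either; that calculation only shows why the shortcut fails.

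Third, larger SDs would hurt the timolol contrasts as well. That stands. Those scenarios bear on the restated power, not on which contrast was chosen, and the conclusion does not depend on them.

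Fourth, the non-randomised status of the controls is openly disclosed. It is, but disclosure does not make either primary comparison randomised.

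**Conclusion.** The plan is wrong as written on this point and must be corrected. It can address the purposes listed in Background and Significance, but it plans no inference on the question in the Research Question and PICO. This follows from the text alone and needs no numerical assumption.

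The stated 80% does not describe the trial's ability to answer its own question. At the protocol's SDs, that ability ranges from 84% to 76% if the regimens differ by 0.05 down to 32% to 27% if they differ by 0.025. These figures rest on assumed differences, on the propranolol and control SDs carrying over to the TID–BID contrast, and on complete 6-month data from 58 infants per arm.

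**What to change.** - **Primary comparison.** Prespecify TID versus BID by randomised arm, awakenings per night at 6 months, reported as a difference with its 95% CI at two-sided alpha 0.05.
- **Timolol comparisons.** Keep BID versus timolol and TID versus timolol as secondary, labelled non-randomised. If the sponsor keeps them as primary aims, make TID versus BID at least co-primary and state the multiplicity rule.
- **Secondary sleep outcomes.** Add TID versus BID to item 1.
- **Analysis paragraph.** Delete the sentence that splits the data into two studies. State that no TID versus BID conclusion will be drawn by comparing the two control-referenced results.
- **Power.** Restate it at 58 per arm for a named, justified TID–BID difference and a justified SD, with the CI half-width from that SD. State that a non-significant result will not be read as equal sleep effects.
- **Consistency.** Bring the Background purposes, Hypothesis, Primary Outcome, Secondary Outcomes and Sample Size into line with the Research Question and PICO. It would also help to say in Study Design which comparison is randomised.

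**Cost.** These are wording changes. The BISQ already goes to all three groups, so no new data are needed, and restating the power adds no patients. The timolol contrasts lose sole primary status. The restated power may be less favourable, depending on the difference chosen: 80% power for 0.025 would need about 205 to 253 per arm at SD 0.09 to 0.10 (t-test), so at 58 per arm the trial should be presented as estimating an effect of that size rather than reliably detecting it.

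Under the co-primary option, if success on any one comparison suffices, an equal Bonferroni split (0.05/3 = 0.0167; an illustration) gives power for 0.05 of 71% to 60% for TID versus BID and lowers each timolol contrast from 80% to 66%. If all comparisons must succeed, no alpha split is needed.
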